7.2.4 Severity

Each adverse event should be assessed for its severity, or the intensity of an event experienced by a subject, using the following:

- **Mild** – events are usually transient, requiring no special treatment, and do not interfere with the subjects daily activities.
- **Moderate** – events that introduce a low level of inconvenience or concern to the subject and may interfere with daily activities, but are usually ameliorated by simple therapeutic measures
- **Severe** – events interrupt a subject's usual daily activity and traditionally require systemic drug therapy or other treatment

The maximum severity observed is to be recorded, except if there is a significant worsening in an AE/ADE severity after device intake, then the change will be tracked as a new AE/ADE record as follows:

- The same wording describing the original AE/ADE must be used.
- Outcome of the initial entry should be designated as 'worsened'.
- The end date of the previous AE/ADE must equal the start date of the new AE/ADE.

7.2.5 Outcome

The outcome should reflect the status of the adverse event at the moment of recording.

- **Resolved without sequelae**- The subject fully recovered from the event without any sequelae. This option also applies when it is unknown whether there are sequelae.
- **Resolved with sequelae** - The subject's condition stabilized despite the persistence of sequelae (e.g., lesion or medical condition which is a consequence of the event). This option does not apply to irreversible congenital anomalies (see under "ongoing").
- **Ongoing** – The subject has not yet recovered from the event. By convention, in the case of an irreversible congenital anomaly, the "Ongoing" option should be chosen and understood as "Not recovered/Not resolved". The same applies to conditions that are not yet resolved, but are controlled by medication (e.g., diabetes, epilepsy) and therefore may not have any symptoms.
- **Worsened** - The severity of the AE/ADE increased.
- **Fatal** – The event is related to a death; whether it caused death or contributed to it. If the subject died of a different cause, prior to resolution of the AE/ADE, the outcome of this AE/ADE should designated "Ongoing", and not "Fatal", and an end date should not be specified.
- **Unknown:** Knowledge of the current status of the AE/ADE is truly not available to the Investigator (i.e. event was ongoing at last observation, but no further contact with the subject could be established). However, all efforts should be made to determine the outcome of any AE, especially that of an SAE/SADE.

7.2.6 Expectedness

If the adverse event is judged to be related to the device, the Investigator will make an assessment of expectedness based on knowledge of the reaction and any relevant product information as documented in the IFU and current protocol. The event will be classed as either;

- **Expected:** the reaction is consistent with the effects of the device listed in the IFU and protocol;
- **Unexpected:** the reaction is not consistent with the effects listed in the IFU and protocol.

The Investigator shall provide rationale for the assessment of the expectedness in a short narrative on the AE/ADE Report Form.

Potential expected adverse events following the application of Emdogain® by type and in order of severity, observed in the clinical trials, are listed below:

Adverse Event type	Adverse Event description
Sensitization	Low rate of sensitization to Emdogain® as a result of repeated use.
Local soft tissue reactions	Local redness, inflammation soreness, gingival irritation, hematoma/ecchymosis, oral candidiasis, tissue necrosis/cratering, angulitis, herpes-like blisters, hypoesthesia (burning and itching reaction on the tongue), oral mucosal reaction, fibrin layer, discoloration.
Local tooth-related reactions	Increased tooth mobility, hypersensitive root surfaces (root sensitivity), pain.
General reactions	Urticaria, itching skin reaction, gastrointestinal disturbances, urogenital disturbances.

Potential expected adverse device effects following the application of PrefGel®:
Reversible and short duration procedure-related dentin hypersensitivity may occasionally occur.

7.3 Procedure for Reporting Adverse Events

Adverse event reporting will begin at the time a subject provides written informed consent and ends after a subject withdraws from the study or completes the final study visit.

For screen failure subjects, any AEs, ADEs, and DDs that occur from the time of informed consent up until the date on which the subject is deemed ineligible for the study will be recorded on a case report form.

Only one AE/ADE Report Form or SAE/SADE Report Form should be completed per event.

To ensure patient confidentiality, the following reports will include the patient number only.

7.3.1 AE Reporting

In the occurrence of an adverse event (AE), the AE/ADE Report Form should be completed in a timely manner. Safety reporting to the Institutional Review Board (IRB) should occur according to the requirements of the local IRB.

7.3.2 SAE Reporting

In the occurrence of a serious adverse event (SAE), expedited reporting requirements are followed. The SAE/SADE Report Form should be completed within 24 hours of awareness of the event and sent to Straumann by fax or email.

Safety reporting to the Institutional Review Board (IRB) should occur according to the requirements of the local IRB.

It is recognized that in many cases SAEs will be treated in a medical rather than a dental environment and the Investigator may not have immediate knowledge of the event. The Investigator should report an SAE as soon as he/she has knowledge of the event within the above time frame irrespective of when the actual event occurred.

7.3.3 DD Reporting

The Investigator should report all Device Deficiencies (DD) by completing the Device Deficiency Case Report Form.

When a device deficiency leads to a potential AE (e.g. bleeding, pain, swelling, infection, peri-implantitis), the AE/ADE Report Form needs to be additionally completed in a timely manner.

Moreover, device deficiencies with SADE potential (e.g. nerve encroachment, sinus perforation, etc.) must be recorded in the SAE/SADE Report Form and follow the expedited reporting requirements (within 24 hours).

7.3.4 ADE Reporting

Adverse device effects (ADE) must be recorded and submitted to Straumann by completing the AE/ADE Report Form in a timely manner. Safety reporting to the Institutional Review Board (IRB) should occur according to the requirements of the local IRB.

7.3.5 SADE Reporting

In the occurrence of a serious adverse device effect (SADE), expedited reporting requirements are followed. The SAE/SADE Report Form should be completed within 24 hours of awareness of the event and sent to Straumann by fax or email.

7.3.6 Additional Safety Reporting

Straumann will report additional safety information to the centers that is relevant to the protocol or study device and may affect the risk/benefit ratio, the rights, safety or welfare of subjects, or the integrity of the study. Such reports may include notification of any changes to the Instructions for Use, any publications or interim reports, or any product recalls.

7.4 Monitoring of Subjects with Adverse Events

Any AE that occurs during the course of this study must be monitored and followed-up by the Investigator until one or more of the following have occurred:

- The AE is resolved,
- Pathological laboratory findings have returned to normal,
- Steady state has been achieved, or
- It has been shown to be unrelated to the study products

It is the responsibility of the sponsor to cooperate with the Investigator to assure that any necessary additional therapeutic measures and follow-up procedures are performed.

8 Statistical Analysis Procedures

The statistical analysis principles described below will be supplemented by a detailed Statistical Analysis Plan (SAP).

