3.1 Type and Design of Study

This study is a post-market, prospective, split-mouth, controlled, multi-center study. Split-mouth design: each patient receives two treatments that are randomly assigned to either the right or left quadrant of the maxillary or mandibular arches.

- *Test Treatment:* Minimally Invasive Scaling and Root Planing (SRP) and applications of Emdogain®
- *Control Treatment:* Minimally Invasive Scaling and Root Planing (SRP) alone

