7.2.2 Relationship to the Study Device

The Investigator should assess the relationship of the adverse event to the study product and study procedure. The relationship should be assessed using the following categories:

- **Definitely Related** – There is a reasonable causal and temporal relationship between the treatment with the study device and the adverse event.
- **Possibly Related** – The relationship between the treatment with the study device and the adverse event is less likely; however, the determination that there is no relationship cannot be made.
- **Not related** – No relationship between treatment with the study device and the adverse event is obvious

NOTE: Device deficiencies that might have led to an SAE are always related to the medical device.

The Investigator shall provide rationale for the assessment of the expectedness in a short narrative on the AE/ADE Report Form.

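### Section 7.4 lets adverse-event follow-up end solely because an event is shown unrelated to the study products, so unresolved control-side or SRP-caused events can leave required follow-up

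*Combined protocol and SAP*

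**What the plan says.** Section 7.4 states that any AE "must be monitored and followed-up by the Investigator until one or more of the following have occurred". Four conditions follow. Three describe the course of the event: resolution, laboratory findings back to normal, and "Steady state has been achieved, or". The fourth describes only its cause: "It has been shown to be unrelated to the study products".

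Section 4.4 names the study products as Emdogain and PrefGel. Section 3.1 defines the control treatment as "Minimally Invasive Scaling and Root Planing (SRP) alone", Section 5.2.2 gives the matching steps, and Section 3.3 restricts PrefGel to the test quadrant.

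Other sections bear on the same events:
- Section 7.1.1 counts events related to the comparator or to the procedures as AEs.
- The classification table after Section 7.1.7 puts device-related and procedure-related events in one column.
- Section 7.2.3 explains the surgical procedure as the application or reapplication of Emdogain.
- Section 7.2.5, in its entry for unknown outcomes, says that "all efforts should be made to determine the outcome of any AE, especially that of an SAE/SADE".

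**The concern.** The study is split-mouth, and one side receives no study product. A stopping condition tied only to the products does not fall evenly on the two sides. A local event confined to the control quadrant can be shown unrelated to Emdogain and PrefGel simply because neither was placed there. The same event on the test side usually cannot.

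SRP and local anesthesia are part of the study treatment in both quadrants but are not study products. An event that they cause can meet the condition on either side.

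Two things are at stake. A patient with an unresolved event from a study treatment may fall outside the required follow-up. And the record of how long such events lasted, and how they ended, may be incomplete. The second matters because the US instructions for use (Appendix 1) say that events due to Emdogain alone could not be distinguished from those of the surgery it accompanies. An SRP-alone quadrant in the same mouth could help to separate them.

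**Working it through.** The documents give no figure on this point and no arithmetic applies. The check sets the rule against each kind of event and then against the other safety text.

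**By kind of event**
1. *Local event, control quadrant only.* No study product was applied (Sections 3.1, 3.3, 5.2.2), so the fourth condition can be met while the event is ongoing.
2. *Event caused by SRP or anesthetic, either quadrant.* The condition can be met if the event is shown unrelated to Emdogain and PrefGel. This applies to both sides.
3. *Event caused by the procedure as Section 7.2.3 defines it.* The procedure there is Emdogain application, so such an event is hard to show unrelated to the product. The condition would rarely be met.
4. *Local event, test quadrant, not shown unrelated.* Follow-up runs to resolution, normal laboratory findings or steady state.
5. *Systemic event.* It cannot be assigned to a quadrant, so no difference between sides arises.

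The gap therefore covers kinds 1 and 2, and the difference between sides arises in kind 1.

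**Against the other safety text**
- *Section 7.1.1 and the classification table* treat comparator and procedure events as part of the safety record. Section 7.4 asks about products only.
- *Section 7.2.3* names Emdogain application and not SRP. An SRP-caused event can therefore be rated unrelated to both product and procedure.
- *Section 7.2.5* asks for the outcome of any AE and sets no condition on relatedness. Section 7.4 allows follow-up to end before an outcome is known. A site cannot fully follow both.
- *Section 5.1.7* has ongoing events reviewed throughout the study, but in the manner that Section 7.4 specifies, so it carries the same gap.
- *The Safety row of the Synopsis* has patients monitored for AEs until the end of follow-up. It does not say how long a known event is followed.
- *Section 11.3.4* expects no outstanding AEs at closeout. It does not say how an event is closed, and closing one under Section 7.4 could satisfy it.

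**How relatedness is decided**
The investigator assesses it (Section 7.2). The investigator or a designee opens the allocation envelope (Section 5.2.1), and no masking of attribution is described. In Section 7.2.2 the Not Related category reads "No relationship between treatment with the study device and the adverse event is obvious". The natural reading is that the absence of an evident link is enough. Possibly Related applies where "the determination that there is no relationship cannot be made". An event with no evident link that cannot be excluded fits both categories.

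**Extent**
Each of the 50 planned subjects has one control and one test quadrant, so 50 of 50 × 2 = 100 study quadrants are control. This counts quadrants, not events. The documents give no AE rate from which to estimate the number affected.

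**The case against.** The strongest reply is that the rest of the safety system catches these events. All AEs are collected from screening (opening of Section 7), and Table 1 has an AE check at every visit to month 12. Both quadrants belong to the same patient and are probed at 3, 6, 9 and 12 months. Section 7.4 itself adds that the sponsor is to cooperate in securing necessary further measures and follow-up. This stands in part: the events are recorded and the patient continues to be seen. It does not say that a known event closed under the fourth condition is tracked to an outcome.

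Several stronger readings are tempting, and the documents do not support them:
- *Control-side events are dropped at once while Emdogain-side events are followed to resolution.* AE checks continue for everyone, and test-side follow-up may also end at steady state or when the event is shown unrelated.
- *A mere judgment ends follow-up.* Section 7.4 says shown and does not cite the Not Related category. Section 7.1.4 also sends any event with even a possible relationship to the adverse device effect class, which narrows the overlap in Section 7.2.2.
- *All procedure-caused events are lost.* Only those from SRP or the anesthetic fit, and they occur on both sides.
- *The safety comparison will be biased against Emdogain.* Section 8.2.3 plans listings and a summary by event category. No comparison of AE duration or outcome by quadrant is described.
- *Control-side events will be coded as recovered.* Section 7.2.5 says of Resolved without sequelae that "This option also applies when it is unknown whether there are sequelae", but that category first requires full recovery. An unresolved event whose follow-up stopped would be Ongoing or Unknown.

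**Conclusion.** The point holds in a limited form. Being unrelated to the study products is enough by itself to end required follow-up, whatever the event's outcome or seriousness. It can be met by an unresolved local control-side event, and by an SRP- or anesthetic-caused event on either side. This conflicts with the instruction on outcomes in Section 7.2.5 and does not match the scope of AEs in Section 7.1.1.

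The consequence is possible incompleteness in AE outcome and duration. AE occurrence, the planned AE summary by category and the primary endpoint are not affected. The size cannot be given, because the documents contain no event rates.

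The conclusion assumes that Section 7.4 uses study products in the sense of Section 4.4, and that sites take Section 7.4 as the governing rule, as Section 5.1.7 directs.

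**What to change.** Reconcile Section 7.4 with the Safety row of the Synopsis and Sections 5.1.7, 7.1.1, 7.2.3, 7.2.5 and 11.3.4, and with the classification table. The result should be that being unrelated to the products alone does not close an unresolved event related to the comparator or to a study procedure, and that study procedure expressly includes SRP.

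Two secondary wording points can go into the same amendment:
- In Section 7.2.2, reword Not Related so that it no longer overlaps Possibly Related and agrees with Section 7.1.4.
- In Section 7.2.5, do not record unknown sequelae of a recovered event as being without sequelae. The Unknown option is currently defined by the event's status, so it would need a small extension to cover this case.

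The cost is a few sentences in a protocol amendment. A few more events would stay open and would be checked at visits already scheduled.

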8.1 Sample Size Calculation

This is a pilot study with a goal to create a standardized treatment workflow that can later be tested in further studies to show that Emdogain® can effectively promote periodontal regeneration as part of the minimally invasive surgical procedure. This study will help to define the selection criteria for clinical preconditions to allow treatment via the envisaged surgical treatment workflow. A sample size of 50 subjects will be adequate for this pilot phase considering a possible dropout rate of up to 15%.

8.2 General Statistical Methods

A qualified statistician using validated statistical software will perform all statistical analysis according to the planned statistical testing provided in the Statistical Analysis Plan (SAP).

95% confidence intervals will be calculated based on the SAP to support the descriptive statistics, where necessary.

Unless otherwise specified, the data will be summarized for non-missing subjects in tables listing the number of subjects, and the mean, 25% percentile, median, 75% percentile minimum, maximum, standard deviation in each treatment group for continuous data (e.g., PPD, GM, CAL, FMPS and pain), or number of subjects and percentage in each treatment group for categorical data (e.g., Bleeding on Probing, Root Dentin Hypersensitivity), as appropriate. In general the denominator for the percentage calculation will be based upon the total number of subjects (N) in the study population, unless otherwise specified.

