2.2 Secondary Objectives

To evaluate the regenerative potential of Emdogain® by looking at differences in:

- Gingival Margin (GM)
- Probing Pocket Depth (PPD)
- Full Mouth Plaque Score (FMPS)
- Bleeding on Probing (BoP)
- Post-surgical pain, and
- Root dentin hypersensitivity

between the test and control treatments.

3 Study Design

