3.4.2 Secondary endpoints

- Change in Gingival Margin (GM)
- Change in Probing Pocket Depth (PPD)
- Change in Full Mouth Plaque Score (FMPS)
- Change in Bleeding on Probing (BoP)
- Change in root dentin hypersensitivity
- Frequency of successful probing points (PPD < 5 mm)
- Number of pockets that would normally be treated surgically that are converted to pockets that do not require surgical intervention

Additional analysis will be done at 3, 6, 9 months post-surgery:

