5.3.5 Full Mouth Plaque Score (FMPS)

The Full Mouth Plaque Score (FMPS) according to O'Leary *et al* should be documented as an indicator for the oral hygiene on each single tooth of the mouth mesial, distal, facial, and lingual.¹² Disclosing agents should not be used to assess plaque.

The FMPS will be assessed with the following formula:

$$\frac{\text{\# of tooth surfaces with plaque}}{\text{total number of tooth surfaces}} \times 100 = \text{FMPS}$$

Assessment will be done at Visit 1, Visit 3 and at the 12-month follow-up visit.

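### The Full Mouth Plaque Score has one value per patient per visit, so the test-versus-control contrast in the secondary objective and the per-group summary is zero by construction

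*Combined protocol and SAP*

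**What the plan says.** **Design.** Section 3.1 states that "each patient receives two treatments that are randomly assigned to either the right or left quadrant of the maxillary or mandibular arches". Each patient therefore supplies both a test and a control quadrant.

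**Definition.** Section 5.3.5 says that FMPS "should be documented as an indicator for the oral hygiene on each single tooth of the mouth mesial, distal, facial, and lingual". The score is the count of surfaces with plaque divided by the "total number of tooth surfaces", times 100. On timing: "Assessment will be done at Visit 1, Visit 3 and at the 12-month follow-up visit".

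**Objective.** Section 2.2, like the synopsis, lists "Full Mouth Plaque Score (FMPS)" among the outcomes whose differences between test and control treatment are to be examined. Section 3.4.2 has the secondary endpoint "Change in Full Mouth Plaque Score (FMPS)", without saying at what level it is analysed.

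**Analysis.**
- Section 8.2 summarises data "in each treatment group for continuous data (e.g., PPD, GM, CAL, FMPS and pain").
- Section 8.2.1 lists FMPS among the baseline data. It then compares baseline variables of interest between the test and control quadrants, by two-sample t-test or Wilcoxon rank-sum test for continuous variables.
- Section 8.3.2 gives the changes in GM and PPD by treatment group and then names the change in FMPS separately, with no grouping.

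**The concern.** A whole-mouth score has no test value and no control value. It pools the test quadrant, the control quadrant and the quadrants outside the study. To fill a table by treatment group, an analyst would have to enter the same number in both columns, and any comparison of those columns carries no information.

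At stake is one stated secondary objective that cannot be answered with the measure chosen for it. A row of identical values, or a baseline test with p = 1, could also be mistaken for evidence that plaque was equal on the two sides. The plan gives conflicting signals on how FMPS is handled: 2.2 and 8.2 treat it as a treatment-level outcome, 8.3.2 as a patient-level one.

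**Working it through.** The plan states no figure for FMPS, so there is none to reproduce. The check is structural.

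**1. Which outcomes in the 2.2 list have a value for each side?**

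| Outcome | Where measured | Value per side? |
|---|---|---|
| GM, PPD, BoP | Teeth in the two contralateral quadrants (5.3.2, 5.3.1, 5.3.4) | Yes |
| Root dentin hypersensitivity | Study tooth (5.3.7) | Yes |
| Pain | Separate right and left scales (Appendix 4) | Yes |
| FMPS | All teeth of the mouth (5.3.5) | No |

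FMPS is the only one without a side-specific measurement.

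**2. The formula.** For one patient at one visit, let P be the surfaces with plaque and S the surfaces present, with subscripts T (test quadrant), C (control quadrant) and O (rest of the mouth):

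FMPS = 100 × (P_T + P_C + P_O) / (S_T + S_C + S_O)

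The value attached to the test side and the value attached to the control side are this same number, so

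test − control = FMPS − FMPS = 0.

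For change from Visit 1 to month 12, both sides share FMPS(12) − FMPS(1), and the difference is again 0. Withdrawal is by subject (5.4.2), so both sides go missing together and the result stands.

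**3. Illustration.** The assumptions, apart from the 50 patients, are not in the documents: 28 teeth × 4 surfaces = 112 surfaces, 28 surfaces in each study quadrant, and the other 56 surfaces with a plaque rate of 30%. Three pairs of true quadrant rates were simulated. Differences are test minus control, in percentage points.

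| True rate, test / control | Expected FMPS | Simulated mean FMPS | FMPS difference (SD) | Simulated quadrant-score difference |
|---|---|---|---|---|
| 30% / 30% | (8.4 + 8.4 + 16.8)/112 = 30% | 30.16 | 0 (0) | +1.0 |
| 20% / 40% | (5.6 + 11.2 + 16.8)/112 = 30% | 29.27 | 0 (0) | −18.8 |
| 10% / 60% | (2.8 + 16.8 + 16.8)/112 = 32.5% | 32.09 | 0 (0) | −50.6 |

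The quadrant score is 100 × P_T/S_T − 100 × P_C/S_C, with expected values 0, −20 and −50. In every scenario the two-sample t-test on FMPS gave t = 0, p = 1, and the rank-sum test gave p = 1. The first two rows have the same expected FMPS of 30% although the side-to-side contrasts differ by 20 points.

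**The case against.** The best defence is section 8.3.2. It is the specific text for the secondary endpoints, and it sets FMPS change apart from the per-group summaries. Section 8.2 is a general default that yields to more specific text and names FMPS only within a list of examples. Section 8.2.1 limits its comparison to variables of interest, and FMPS may not be one. Section 8 also leaves detail to a Statistical Analysis Plan, and no separate text of that plan appears in the material available. A competent statistician would notice two identical columns.

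Much of this stands. Section 8.3.2 is a real mitigation, and the visible text plans no FMPS hypothesis test at follow-up, so a misleading null report is a possibility and not a planned result. What the defence does not reach is the objective: 2.2 and the synopsis ask for a treatment difference in FMPS, and no reading of 8.3.2 supplies one. Section 8.2 also names FMPS explicitly as a per-group variable, and an analysis plan built on these sections would inherit the conflict.

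A reader might infer more, namely that unmeasured side-to-side plaque confounds the CAL comparison. The documents do not support that. Side is randomised within patient (3.1, 5.2.1), both study quadrants receive supragingival plaque removal at Visit 3 (5.2.3), and hygiene instructions are given per subject (5.2.4). Plaque at Visit 3 and month 12 is measured after treatment and could itself be affected by it, so it is not simply a confounder.

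**Conclusion.** The conflict is real and limited. By the plan's own formula and design, the test-minus-control FMPS difference is 0 in 100% of patients at all three visits and for change. This rests only on sections 3.1 and 5.3.5; the simulated plaque rates merely illustrate it. The statement is conditional: it describes what happens if the whole-mouth value is assigned to both sides, which is the only way to follow 2.2 and 8.2 literally. It is not an estimate of bias in any other outcome.

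The text at fault is the secondary objective (synopsis and 2.2), the per-group summary (8.2) and, if FMPS counts as a variable of interest, the baseline comparison (8.2.1). Sections 3.4.2 and 8.3.2 work if read at patient level. The primary endpoint and the sample size do not depend on FMPS. The text should be reconciled before analysis, but this is not a defect that threatens the main conclusion.

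**What to change.** **Minimum change, wording only.** Report FMPS once per patient at Visit 1, Visit 3 and month 12, as an oral hygiene descriptor. Remove it from the between-treatment objective (synopsis and 2.2), from the per-group examples in 8.2 and from the baseline balance test in 8.2.1. State in 8.3.2 that its change is summarised per patient. The endpoint in 3.4.2 can then stay.

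**If a side-specific plaque comparison is wanted.** Section 5.3.5 calls for plaque to be documented on four surfaces of every tooth. If those records were retained, derive for each study quadrant 100 × surfaces with plaque / surfaces present. Analyse its change as a within-patient paired difference, and label it an added descriptive outcome. The label matters because follow-up was planned to end by December 2017, while this protocol is Version 5.0 of 29-Mar-2018.

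**Cost.** The first option costs a few lines of text. The second costs one derived variable and one more secondary comparison. It may also require entering surface data from source records: the plaque case report form is not shown, so it cannot be assumed that the database holds more than the percentage. If the surface records no longer exist, only the first option is available.
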